## Statistical Analysis Plan

Sponsor Name: Golden Biotechnology Corporation  
Sponsor Protocol ID: GH Covid-2-001

Covance Study ID: 000000203201

than the ones mentioned above, planned last treatment date is either the day 14 date or the end of study date, whichever occurs first.

Percentage compliance will be summarized descriptively by treatment group for the SS. The number and percentage of compliant patients will be presented for the SS, where compliant is defined as percentage compliance between 80.0% and 120.0% inclusive. The following percentage compliance categories will also be presented:

- <50.0%
- $\geq 50.0\%$  and  $<80.0\%$
- $\geq 80.0\%$  and  $\leq 120.0\%$
- $>120.0\%$

### 7.7.2 Adverse Events

All adverse events (AEs) recorded on the eCRF will be coded using the MedDRA dictionary [Version 23.0 dated 19 Apr 2020 or a later version if updated during the study (exclusively meant for COVID-19)] and classified as either pre-treatment AEs or treatment – emergent AEs (TEAEs) as follows:

- Pre-treatment AEs are events that start after the signing the informed consent form and prior to the date of first dose of study treatment.
- TEAEs are events with start date on or after the date of first dose of study treatment and up to 2 weeks after date of last dose of study treatment or events with start date prior to the date of first dose of study treatment whose severity worsens on or after the date of first dose of study treatment.

If an AE can't be classified as pre-treatment AE or TEAE due to missing/partial dates, it will be classified as TEAE.

The number and percentage of patients reporting each pre-treatment AE will be summarized for each treatment group and overall, by System Organ Class (SOC) and Preferred Term (PT) for SS.

All AE data will be listed by treatment group and overall. Treatment-emergence status will be flagged in the listing. In addition, corresponding listings of serious AEs (SAEs), treatment-related AEs, AEs leading to discontinuation of study treatment, AEs leading to discontinuation of study and AEs resulting in death will be produced for the SS.

The severity of all AEs is recorded as mild, moderate, or severe. If severity is missing for a TEAE, it will be considered severe only in the overall category in the summary tables.

The relationship between an AE and treatment is assessed as related, possibly related, unlikely related, or not related. A treatment-related AE is an AE considered by the investigator as related or possibly related to treatment or with missing relationship to treatment.

An overview table will summarize the number and percentage of patients with at least one of the following TEAEs, along with the number of corresponding TEAEs, where

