14. Treatment with any antiviral drugs (except remdesivir or other authorized treatments for COVID-19), or with any drugs known to be strong inducers or inhibitors of cytochrome P450 isoform (CYP) 2C19, CYP3A4, CYP2C8, and CYP2E1 within 14 days or 5 half-lives prior to the start of study treatment. Drugs with a narrow therapeutic index that are substrates of 1A2, 2B6, 2C8, 2C9, 2C19, 3A, and 2D6 are also prohibited.

15. Inability to swallow oral medications or a gastrointestinal disorder with diarrhea (eg, Crohn's disease), malabsorption, or diarrhea of any etiology at baseline.

16. Any other clinically significant medical condition or laboratory abnormality that, in the opinion of the investigator, would jeopardize the safety of the patient or potentially impact patient compliance or the safety/efficacy observations in the study.

Test product, dose, and mode of administration:

Antroquinonol in a dose of 100 mg (1 capsule) administered BID orally, for 14 days.

Reference therapy, dose, and mode of administration:

Placebo (1 capsule) administered BID orally, for 14 days.

Duration of patient participation in study:

Total duration of patient participation is planned to be a maximum of 33 days.

The screening period is planned to be up to 3 days. The planned study treatment duration is 14 days.

Follow-up/EOS assessments will be performed on Day 28 (± 2 days).

Study populations:

Intention-to-treat (ITT): All randomized patients. Patients will be analyzed according to the treatment to which they were randomized.

modified ITT (mITT): All randomized patients who received at least 1 dose of study drug.

Per Protocol Set (PPS): All patients from the ITT set who have no important protocol deviations during the study. Patients with any important protocol deviations shall be excluded from the PPS prior to database lock.

Safety Set (SS): All patients who have received at least 1 dose of the study treatment. Patients will be analyzed according to the study treatment they actually received.

Pharmacokinetic Set (PKS): Patients in the sentinel cohort who have received at least 1 dose of the study treatment and have at least 1 evaluable plasma concentration without important protocol deviations or events thought to significantly affect the PK.

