4.4.2. Hepatic injury or renal impairment

4.4.2.1. *Hepatic injury*

Discontinuation of study treatment for abnormal liver tests should be considered by the investigator when a patient meets one of the conditions outlined in [Figure 2](#) or if the investigator believes that it is in the best interest of the patient.

Figure 2: Stopping Criteria for Liver Injury

Abbreviations: ALT = alanine aminotransferase; INR = international normalized ratio; ULN = upper limit of normal
 Note: INR value is not applicable to patients on anticoagulants.

4.4.2.2. *Renal impairment*

If a patient has renal impairment (creatinine clearance <50 mL/min), treatment should be discontinued.

4.4.3. **Discontinuation of study treatment**

A patient may be discontinued early from study drug treatment (ET of study treatment) for the following reasons:

- Lack of efficacy (e.g. patients who require nonstudy antiviral or anticytokine therapy due to progression of COVID-19), and the investigator's decision. Note: remdesivir or other authorized treatments for COVID-19 is allowed if considered SoC, if started prior to randomization or during the study. Initiation of remdesivir or other authorized treatments for COVID-19 during the study will be considered a treatment failure if started due to progression of disease.
- Adverse event
- Withdrawal by patient (specify reason in the eCRF)
- Lost to follow-up
- Death

- Physician decision (i.e. investigator decision based on protocol deviation, assessment that it is not in the patient's best interest to continue, or other reason [specify reason in the eCRF]).
- Sponsor decision (specify reason in the electronic case report form [eCRF])

No temporary treatment discontinuation is permitted.

Patients who discontinue study treatment prematurely will be asked about the reason(s) for discontinuation and will be asked to continue all assessments up to Day 28. Patients will be educated about the continued scientific importance of their data and encouraged to complete the Day 28 Follow-up/EOS assessments even if they discontinue study treatment prematurely.

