7.2. Safety Assessments

7.2.1. Adverse events

7.2.1.1. *Definitions*

Adverse event definitions and assignment of severity and causality are detailed in [Appendix 1](#).

Adverse events will be elicited from the patient (or, when appropriate, from a caregiver, surrogate, or the patient's legally authorized representative) by the study site staff using a nonleading question such as "How are you feeling today?" or "Have you had any health concerns since your last visit?"

The investigator and any designees are responsible for detecting, documenting, and reporting events that meet the definition of an AE or SAE and remain responsible for following up AEs that are serious, considered related to the study treatment or the study, or that caused the patient to discontinue the study treatment.

Adverse events will be assessed from signing the ICF until 2 weeks after the last dose of study treatment (Day 28 ± 2 days) as noted in the Schedule of Assessments table ([Appendix 5](#)).

Adverse events will be coded according to the Medical Dictionary for Regulatory Activities (MedDRA) version 23.0 dated 19 April 2020 (exclusively meant for COVID-19) or later.

7.2.1.2. *Reporting serious adverse events*

Serious AE reporting will be carried out as per local/country regulations, and will be described in the Safety Management Plan.

All SAEs occurring after the signing of the ICF until 30 days following last dose of the study treatment and regardless of study treatment relationship, must be reported to Covance within 24 hours of obtaining knowledge of the event. The report should include all available information requested on the SAE form.

Serious AEs - Covance PSS

E-mail: [contact] (standard)

The SAE form will collect data surrounding the event (eg, the nature of the symptom[s], time of onset in relation to initiation of therapy, duration, intensity, and whether or not therapy was discontinued). The investigator's assessment of the probable cause of the event will also be included. In addition, relevant medical history, concomitant medications, laboratory and diagnostic tests reports, and procedures as well as all pertinent medical information related to the event will also be collected.

Covance PSS will forward SAE queries requesting incomplete or missing information directly to the investigator. It is the investigator's responsibility to be diligent in providing this information back to Covance PSS as soon as it is available.

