10. APPENDICES

Appendix 1. Adverse Event Definitions

Definitions

An adverse event (AE) is any untoward medical occurrence associated with the use of a drug in humans, whether or not considered drug related. This includes the following:

- Any clinically significant worsening of a pre-existing condition.
- Any recurrence of a pre-existing condition.
- An AE occurring from overdose of a sponsor study drug whether accidental or intentional (ie, a dose higher than that prescribed by a health care professional for clinical reasons).
- An AE occurring from abuse of a sponsor study drug (ie, use for nonclinical reasons).
- An AE that has been associated with the discontinuation of the use of a sponsor study drug.
- Clinically significant laboratory abnormalities (i.e. the laboratory abnormality is associated with symptoms, requires medical intervention, or requires changes to study drug treatment).

Note: A procedure is not an AE, but the reason for a procedure may be an AE.

A pre-existing condition is a clinical condition (including a condition being treated) that is diagnosed before the patient signs the informed consent form and that is documented as part of the patient's medical history.

The questions concerning whether the condition existed before the start of the active phase of the study and whether it has increased in severity and/or frequency will be used to determine whether an event is a treatment-emergent AE. An AE is considered to be treatment-emergent if (1) it is not present when the active phase of the study begins and is not a chronic condition that is part of the patient's medical history, or (2) it is present at the start of the active phase of the study or as part of the patient's medical history, but the severity or frequency increases during the active phase. The active phase of the study begins at the time of the first dose of the study drug. The active phase of the study ends at the Day 28 Follow-up/End of Study (EOS) visit.

Disease-specific signs and symptoms that were ongoing prior to study entry will not be considered AEs unless they worsen (eg, increase in frequency or severity) unexpectedly during the course of the trial.

Reporting of Adverse Events

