At each visit the investigator, or delegate, will determine whether or not any AEs have occurred. Nonleading questions such as "How are you feeling today?" or "Have you had any health concerns since your last visit?" should be used to elicit the patient to report any possible AEs. If any AEs have occurred, they will be recorded in the AE section of the electronic case report form (eCRF) and in the patient's source documents. If known, the diagnosis should be recorded, in preference to listing the individual signs and symptoms.

Adverse event reporting begins from the time of informed consent and ends 2 weeks after the last dose of study treatment (Day 28 ± 2 days).

Assessment of Severity

The investigator will be asked to provide an assessment of the severity of the AE using the following categories:

- **Mild:** Usually transient and may require only minimal treatment or therapeutic intervention. The event does not generally interfere with usual activities of daily living.
- **Moderate:** Usually alleviated with additional specific therapeutic intervention. The event interferes with usual activities of daily living, causing discomfort but poses no significant or permanent risk of harm to the patient.
- **Severe:** Interrupts usual activities of daily living, significantly affects clinical status, or may require intensive therapeutic intervention.

Relationship to Study Treatment

The investigator will make a determination of the relationship of the AE to the study drug using a 4-category system according to the following guidelines:

- **Not related:** When the AE is definitely caused by the patient's clinical state, or the study procedure/conditions.
- **Unlikely Related:** When the temporal association between the AE and the drug is such that the drug is not likely to have any reasonable association with the AE.
- **Possibly Related:** When the AE follows a reasonable temporal sequence from the time of drug administration but could have been produced by the patient's clinical state or the study procedures/conditions.
- **Related:** When the AE follows a reasonable temporal sequence from administration of the drug, abates upon discontinuation of the drug, and follows a known or hypothesized cause-effect relationship.
- If causality is assessed as Related or Possibly Related, the event will be considered as related for regulatory reporting purposes.

Action Taken for Adverse Events

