- b Initial sentinel cohort of 20 patients to be enrolled to assess safety, tolerability, efficacy, and PK. Enrollment will pause after the 20th patient in the sentinel cohort has started treatment, until the results of the interim analysis are known. Once the 20th patient in the sentinel cohort has completed 14 days of treatment, an unblinded DMC will assess the safety, tolerability, efficacy, and PK of 100 mg BID antroquinonol in COVID-19 patients in the sentinel cohort (interim analysis 1). The DMC will issue a recommendation to enroll patients for the expansion cohort, or to stop the study depending on the safety and futility assessment. Once the 80th patient has been enrolled and completed 14 days of treatment, the DMC will review the safety, tolerability and efficacy data (interim analysis 2). Enrollment may be restricted at the 100th patient until the DMC has completed the assessment to prevent excessive enrollment.
- c Patients must satisfy all of the criteria at the screening visit unless otherwise stated (e.g. some criteria can be evaluated at Day 1 if needed).
- d Daily study treatment administration from Day 1 to Day 14.
- e A complete physical examination (general appearance, HEENT, lymphatic, cardiovascular, respiratory, gastrointestinal, musculoskeletal, neurological, and dermatological systems) will be performed at screening. Vital signs (respiratory rate, temperature, blood pressure, and pulse rate) to be assessed during hospitalization, on discharge, ET/EOT and Follow-up/EOS visit (for site or in-person visits only). Pulse oximetry to measure SpO₂ will be collected in the eCRF at screening (room air) after screening with vital

signs (Day 1; Day 3, Day 5, Day 7, Day 14/EOT and/or Discharge/ET visits, Day 28 if patient is in hospital). FiO₂ data will be collected the same days as vital signs. PaO₂ will be collected if done as part of the standard of care. Height and body weight will be measured only at screening. After patient is discharged from hospital, SpO₂ should be collected at Day 5 and Day 14 if visits completed in clinic/hospital. Values collected by a home health provider may be utilized, but are not required (refer to [Section 7.2.4.2](#)). Body temperature will be measured according to site's local practices and may include oral, tympanic, rectal, axillary, or frontal.

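### SAP 7.7.2 closes the TEAE window 14 days after the last dose, protocol Appendix 1 closes it at the Day 28 visit, and the two disagree for patients who stop treatment early

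*SAP*

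**What the plan says.** **Protocol, Appendix 1 (definitions).** Treatment emergence is tied to an active phase. "The active phase of the study begins at the time of the first dose of the study drug", and "The active phase of the study ends at the Day 28 Follow-up/End of Study (EOS) visit". The last-dose date plays no part.

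**Protocol, 7.2.1.1 and Appendix 1 (reporting of AEs).** AE reporting starts at consent and "ends 2 weeks after the last dose of study treatment (Day 28 ± 2 days"; section 7.2.1.1 gives the same period. Both treat the last-dose limit and the Day 28 visit as one time point.

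**Protocol, 4.4.3, 7.2.1.2 and Appendix 5.** Stopping treatment is permanent, and patients who stop early "will be asked to continue all assessments up to Day 28". AE assessment is scheduled at the Day 28 visit. The SAE period is longer: "All SAEs occurring after the signing of the ICF until 30 days following last dose of the study treatment".

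**SAP, 7.7.2.** AEs have two classes only, pre-treatment and treatment-emergent. A new event is treatment-emergent if it starts on or after first dose and "up to 2 weeks after date of last dose of study treatment". There is no post-treatment class. The overview table, with its SAE and death rows, is limited to TEAEs. The SOC/PT summaries are headed simply as AEs. All AEs are listed with a treatment-emergence flag.

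**SAP, section 8.** No change of statistical method from the protocol is declared.

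**The concern.** Treatment emergence decides which events enter the overview table that most readers will use to compare the arms. Under the protocol definition every treated patient is observed over the same period, from first dose to the Day 28 visit. Under the SAP definition the period depends on when the patient stopped, while the denominator stays the full Safety Set. Reasons for stopping in Protocol 4.4.3 include adverse events and lack of efficacy, so early stoppers are unlikely to be a random sample.

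If the arms differ in how often or how early patients stop, their TEAE percentages describe windows of different length. An SAE on Day 20 after a last dose on Day 3 shows the problem. It is reportable under Protocol 7.2.1.2 and is a TEAE under Appendix 1, yet under the SAP it is neither a pre-treatment AE nor a TEAE.

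**Working it through.** **Inputs.**
- Planned dosing: "Daily study treatment administration from Day 1 to Day 14" (Protocol Appendix 5).
- Final visit: Day 28 ± 2, that is Days 26 to 30 (Protocol synopsis; SAP 6.1).
- SAP window end: last dose + 14 days (SAP 7.7.2).
- Protocol window end: the Day 28 visit (Protocol Appendix 1).

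**Step 1: reproduce the protocol's equation of the two limits.** For a last dose on Day d, the SAP window closes on Day d + 14. With d = 14 it closes on Day 14 + 14 = Day 28, so the equation holds for a patient who completes treatment. For d + 14 to reach the visit window, d must be at least 26 − 14 = 12. The equation therefore fails, even with the ± 2 days, for any last dose before Day 12.

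**Step 2: days covered by the protocol but not by the SAP.** The gap is (visit day) − (d + 14), or 0 if that is negative.

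| Last dose (Day d) | SAP window closes | Gap, visit on Day 26 | Gap, visit on Day 28 | Gap, visit on Day 30 |
|---|---|---|---|---|
| 1 | Day 15 | 11 | 13 | 15 |
| 3 | Day 17 | 9 | 11 | 13 |
| 5 | Day 19 | 7 | 9 | 11 |
| 7 | Day 21 | 5 | 7 | 9 |
| 10 | Day 24 | 2 | 4 | 6 |
| 12 | Day 26 | 0 | 2 | 4 |
| 14 | Day 28 | 0 | 0 | 2 |

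For a visit on Day 28, a Day 3 stop leaves Days 18-28 uncovered (11/28 = 39% of the period) and a Day 7 stop leaves Days 22-28 (7/28 = 25%). For completers the difference is at most 2 days, which is within the visit tolerance.

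**Step 3: where the events go.** A dated new event in the gap belongs to neither SAP class, so it leaves the overview table. Two kinds of event are not lost. AEs that cannot be classified because of missing or partial dates default to TEAE, and the limb for pre-dose events that worsen has no end date.

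The effect on the SOC/PT tables depends on whether AE there means TEAE. The overview rows use AE in that sense, and Protocol 8.5 specifies TEAEs for most of these tables but leaves SAEs unqualified. The SAP does not say.

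**Step 4: number of patients.** The documents give no rate of early treatment discontinuation for this trial. The 2% drop-out allowance in Protocol 8.1 is a sample-size input and does not describe stopping treatment. As an assumption, early-stop rates of 2%, 5%, 10% and 15% of 174 give 3.5, 8.7, 17.4 and 26.1 patients, so about 3 to 26. This counts every early stop, including Day 12-13 stops that lose only 1-2 days for a visit on Day 28, and patients who die, who lose nothing after death.

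**The case against.** **The SAP wording comes from the protocol.** This is correct. SAP 7.7.2 follows the AE reporting period in Protocol 7.2.1.1 and Appendix 1. The protocol is inconsistent with itself for early stoppers, so correcting the SAP alone would leave that conflict. It also means the late data are not secure: read literally, the reporting period closes non-serious AE collection 14 days after the last dose, although Protocol 4.4.3 and the schedule run to Day 28.

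**A fixed interval after last dose is a legitimate convention.** In general it is. The protocol reports half-lives of 1.30 to 4.33 hours and an effective 7.643 hours on repeated dosing, so 14 days (336 hours) is 336/7.643, or about 44 half-lives. But Appendix 1 chose a different definition, and the SAP departs from it without saying so.

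**A reader might infer that every safety table loses these events.** The text supports this only for the overview table. For the SOC/PT tables it is a plausible reading that the SAP does not state. The events also remain in the flagged listings, including the SAE and death listings, and SAP 7.6.2.4 compares deaths on Days 7, 14 and 28 whatever the last-dose date.

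**A reader might infer that the rule understates harm from antroquinonol.** The documents do not show this. If more placebo patients stop for lack of efficacy, truncation removes placebo events instead. Appendix 1 also exempts respiratory failure due to COVID-19 from AE reporting unless judged drug-related, and expected disease progression unless more severe than expected, so much of the progression after stopping would be absent under either window.

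**A reader might take a stop rate from the hyperlipidemia study** (Protocol 1.2.3), where 15 of 120 subjects stopped for AEs, and obtain 0.125 × 174, or about 22 patients. That rate accrued over 12 weeks in another population with once-daily dosing and includes placebo. Scaled to 14 of 84 days under a constant hazard, as an assumption, it is 1 − 0.875^(1/6) = 2.2%, or about 4 patients. Other reasons for stopping would add to this by an unknown amount.

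**Conclusion.** The inconsistency is real. For a patient whose last dose falls before Day 14 and whose visit is on Day 28, the SAP window closes 14 − d days before the protocol's, and new events in that gap leave the TEAE overview table without a declared change from the protocol. For last doses on Day 12 or 13 the gap is 1-2 days. It matters mainly for stops in the first week, where 7 to 13 days are lost.

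The consequence is an observation window that can differ between arms. Its direction cannot be known in advance, and its size depends on an early-stop rate that the documents do not give (about 3-26 patients under the assumed 2-15%). The events remain on record in the listings, deaths are compared separately, and the safety analysis involves no formal testing. This point therefore concerns the comparability and consistency of the tables. It does not show that harm is concealed. It should be corrected because one definition has to govern and the correction is small.

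**What to change.** 1. In SAP 7.7.2, define TEAEs as events that start or worsen from first dose through the Day 28 Follow-up/EOS visit, for all treated patients, as in Protocol Appendix 1.
2. In Protocol 7.2.1.1 and the reporting paragraph of Appendix 1, reconcile the AE reporting period with the active-phase definition, so that AE collection in patients who stop early clearly runs to Day 28.
3. In SAP 7.7.2, state whether the SOC/PT tables are TEAE tables, so that they can be reconciled with the overview table.
4. If a window tied to dosing is wanted, keep a table of events up to 14 days after the last dose as a labelled supplement. If that window is kept as the main one instead, add a post-treatment AE class with its own table and record the departure in SAP section 8.

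The cost is SAP wording, one derivation and a protocol clarification. No visits are added, since AE assessment at Day 28 is already scheduled. Sites should be asked whether non-serious AEs in early stoppers have in fact been recorded to Day 28, because the present reporting wording can be read as ending sooner.
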